6.1 Eribulin dosing delays/dose modifications

Participants should be carefully monitored for toxicity. If a treatment delay is required for eribulin toxicity or if treatment with eribulin is withheld permanently, treatment with pembrolizumab is allowed. Dosing levels for eribulin are shown in Table 2. Eribulin toxicities should be managed according to the guidelines in Tables 3.1 through 3.5. Once reduced, the dose of eribulin will not be re-escalated.

Clinical judgement should be used to determine appropriate management of the patient during any adverse event. Temporary interruption, dose reduction or permanent discontinuation of Eribulin should be considered if clinically indicated.

Table 2. Eribulin dosing levels

Dose Level	Eribulin Dose
Starting dose	$1.4\text{mg}/\text{m}^2$ (1 cycle = 21 days)
1 st dose reduction	$1.1\text{ mg}/\text{m}^2$
2 nd dose reduction	$0.7\text{ mg}/\text{m}^2$

- Toxicities graded in accordance with National Cancer Institute Common Toxicity Criteria for AEs, version 5.0
- Discontinuation of eribulin is required if a dose reduction to less than $0.7\text{ mg}/\text{m}^2$ is required.
- A minimum of 6 days between Day 1 and Day 8 of eribulin administration will be required. Day 8 administration of Eribulin must not be given prior to Day 8. A minimum of 13 days between Day 8 and Day 1 of next cycle will be required.
- If a participant does not meet criteria to receive Day 8 of eribulin, the Day 8 dose should be skipped (i.e., it will not be made up on Day 15) for that cycle.
- Once a dose is reduced, it should not be re-escalated.
- Treatment with eribulin will be discontinued if participants require a delay greater than 5 weeks.
- QTc prolongation has been observed in patients receiving eribulin. Cardiac monitoring, including EKG, will be performed per institutional standard of care.

Table 3.1 Eribulin Diarrhea Toxicity Dose Modification

Diarrhea	Management/Next Dose for Eribulin
≤ Grade 2	No dose modification

Diarrhea	Management/Next Dose for Eribulin
Grade 3, first occurrence	Hold eribulin until recovery to grade < 2. Maximize supportive care measures. If symptom recovery occurs within 1 week, then eribulin may be resumed at the same dose if deemed appropriate by the investigator, otherwise, reduce by 1 dose level.
Grade 3, despite maximal supportive measures	Hold eribulin until recovery to grade < 2 then reduce by 1 dose level.

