Grade 4	Hold eribulin until recovery to grade < 2 then reduce by 1 dose level.

Table 3.2 Eribulin Peripheral Neuropathy Dose Modification

Peripheral Neuropathy	Management/Next Dose for Eribulin
≤ Grade 1	No dose modification
Grade 2	For intolerable (as determined by physician and participant) grade 2, decrease eribulin by one dose level.
Grade 3	Hold eribulin until recovery to grade < 2 then reduce by 1 dose level.
Grade 4	Permanently discontinue eribulin.

Table 3.3 Eribulin Neutropenia Dose Modification

Neutropenia	Management/Next Dose for Eribulin
ANC < 500 cells/mm ³ lasting > 7 days with or without use of growth factors	Hold eribulin until recovery to grade < 2 and reduce by 1 dose level. Prophylactic growth factor support should be instituted for subsequent cycles.
ANC < 500 cells/mm ³ lasting ≤ 7 days without use of growth factors	Hold eribulin until recovery to grade < 2. Resume eribulin at the same dose. Growth factor support should be provided.
ANC < 500 cells/mm ³ lasting ≤ 7 days in despite use of growth factors	Hold eribulin until recovery to grade < 2, and reduce by 1 dose level. Continue ongoing prophylactic growth factor support for subsequent cycles.
ANC < 1000 /mm ³ with fever or infection without use of growth factors	Hold eribulin until recovery to grade < 2. Resume eribulin at the same dose. Growth factor support should be provided.
ANC < 1000 /mm ³ with fever or infection despite use of growth factors	Hold eribulin until recovery to grade < 2, and reduce by 1 dose level. Growth factor support should be provided.
ANC < 1000 /mm ³ without fever or infection	First occurrence: Hold eribulin until recovery to grade < 2 then resume at the same dose. Growth factor support should be provided. If uncomplicated neutropenia (<1000 /mm ³ without fever or infection) occurs/recurs despite growth factor support, then hold eribulin until recovery to grade < 2. Eribulin may be then be resumed at the same dose with growth factor support, or it may be reduced by one dose level. If a participant misses two consecutive Day 8 eribulin doses due to uncomplicated neutropenia, then hold eribulin until

Neutropenia	Management/Next Dose for Eribulin
	recovery to grade < 2, reduce by 1 dose level, and consider prophylactic growth factor support for subsequent cycles.
ANC = absolute neutrophil count	

Table 3.4 Eribulin Thrombocytopenia Dose Modification

Thrombocytopenia	Management/Next Dose for Eribulin

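### Table 3.3 gives two opposite next-dose instructions for an ANC below 500 that lasts more than 7 days without growth factor

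*Combined protocol and SAP*

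**What the plan says.** Section 6.1 sends investigators to Tables 3.1 to 3.5 for eribulin toxicities. Table 3.3 covers neutropenia in six rows, numbered here from the top.

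- Row 1: ANC below 500 "lasting > 7 days with or without use of growth factors". Hold, then go down one dose level.
- Rows 2 and 3: ANC below 500 for 7 days or less. Without growth factor (row 2), same dose. Despite growth factor (row 3), reduce.
- Row 4: ANC below 1000 "with fever or infection without use of growth factors". Hold, then same dose.
- Row 5: as row 4 but despite growth factor. Hold, then reduce.
- Row 6: ANC below 1000 with neither fever nor infection. The opening clause reads "First occurrence: Hold eribulin until recovery to grade < 2 then resume at the same dose". Later clauses cover events despite growth factor and two consecutive missed Day 8 doses.

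The notes to Table 2 set dose levels of 1.4, 1.1 and 0.7 mg/m², rule out re-escalation, and stop eribulin if a dose below 0.7 would be needed.

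**The concern.** Rows 4 to 6 have no lower ANC limit and no duration limit. Any ANC below 500 is also below 1000, so an event in rows 1 to 3 can also fall in rows 4 to 6. For deep, prolonged neutropenia without growth factor, the overlapping rows give opposite instructions.

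Two investigators following the same table could give different next doses after the same event, and neither would be deviating from the protocol. Read literally, row 4 would return a participant with deep, prolonged, febrile neutropenia to full dose. In the other direction, a reduction made under row 1 is permanent.

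**Working it through.** No power or error-rate figure bears on this point. The check sets the rows side by side, looks for a rule that ranks them, and then sizes the difference in dose.

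**Step 1. Which rows match?** Take ANC below 500 for more than 7 days with no growth factor in use.

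| Situation | Rows met | Next dose after the hold |
|---|---|---|
| Fever or infection | 1 and 4 | Row 1: one level lower. Row 4: same dose |
| No fever or infection, first occurrence | 1 and 6 | Row 1: one level lower. Row 6: same dose |

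Rows 2 and 3 drop out because they need 7 days or less. Row 5 drops out because it needs growth factor in use. With growth factor in use and fever or infection, rows 1 and 5 agree on a reduction. At ANC 500 to 999 only rows 4 to 6 apply, and they do not conflict.

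**Step 2. Does any text rank the rows?** Neither Section 6, Section 6.1 nor the table footnote does. The clinical-judgement sentence in Section 6.1 allows a reduction but does not say which row prevails. Section 6.2 refers expected eribulin-related hematologic events back to the eribulin tables. The grade 4 rules in Section 5.5 concern stopping treatment, not the dose on resumption.

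**Step 3. When can it arise?** Rows 1 to 5 and the opening clause of row 6 all call for growth factor after the event. Section 5.4.2 allows primary prophylaxis at the investigator's discretion. If these are followed, an event without growth factor is essentially the first neutropenia event in a participant not given prophylaxis.

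**Step 4. How large is the difference?** Dose levels are from Table 2.

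- From the starting dose: (1.4 − 1.1)/1.4 = 0.3/1.4 = 21.4%.
- After one earlier reduction: (1.1 − 0.7)/1.1 = 0.4/1.1 = 36.4%.
- At 0.7 mg/m²: stay at 0.7 or stop eribulin.

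The last two need earlier reductions for other toxicities, or growth factor not given as directed.

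**Step 5. Other overlaps.** These add little, but the fix should cover them.

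- ANC below 500 with growth factor in use, no fever or infection: rows 1 and 3 require a reduction, while row 6 leaves it optional ("Eribulin may be then be resumed at the same dose with growth factor support, or it may be reduced by one dose level"). Reducing satisfies both.
- ANC below 500 for up to "7 days without use of growth factors", at a second consecutive missed Day 8 dose: row 2 says same dose, while row 6 ("If a participant misses two consecutive Day 8 eribulin doses due to uncomplicated neutropenia, then hold eribulin until" recovery) goes on to "reduce by 1 dose level, and consider prophylactic growth factor support for subsequent cycles". Day 8 doses are missed through the Table 2 note, "If a participant does not meet criteria to receive Day 8 of eribulin, the Day 8 dose should be skipped". This arises only if growth factor was not in use at the second event, although rows 2 and 6 call for it after the first.

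**The case against.** The best reply is that row 1 was plainly meant to govern. Events of 7 days or less are split by growth-factor use, whereas row 1 covers both, so the drafters considered prolonged neutropenia without growth factor and chose reduction. Every such event either has fever or infection (row 4) or does not (row 6). If those rows prevailed, the without-growth-factor half of row 1 would cover almost nothing except a recurrent uncomplicated event still without growth factor. Section 6.1 also describes the tables as guidelines, so an investigator who reduces under row 1 breaches nothing.

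This stands as evidence of intent, and the fix below follows it. It does not supply the missing rule. Specificity does not settle the matter either: row 1 is narrower on depth and duration, row 4 is narrower on fever or infection and on absence of growth factor, and neither contains the other.

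The effect is also limited in practice, and that stands. Every row holds eribulin until recovery below grade 2, and rows 1, 4 and the opening clause of row 6 all call for growth factor. Section 1.1 plans blood counts before each drug administration, so documenting an uncomplicated ANC below 500 for more than 7 days would usually need extra counts.

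**Conclusion.** The contradiction is real, and it is a minor one. It concerns ANC below 500 for more than 7 days without growth factor, mainly at the first event. Its usual size is one dose level, 1.4 against 1.1 mg/m² (21%), without re-escalation. This assumes the starting dose and that growth factor is given as the table directs. Sample size, power and the primary analysis are unaffected.

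A reader might infer two stronger things that the documents do not support.

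- That about 7 participants are exposed. Section 2.5.2.5 reports grade 4 neutropenia lasting more than a week in 12% of eribulin participants in a phase III trial (identified in the reference list as metastatic breast cancer), and 0.12 × 57 = 6.84. Even assuming grade 4 means ANC below 500, a band the documents do not print, this does not measure the conflict. It comes from another disease, growth-factor use behind it is not given, and the share without growth factor here is unknown. No count can be estimated.
- That the 36% step or stopping eribulin is a typical consequence. Both depend on the conditions in Step 4 and should be uncommon.

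**What to change.** Add a footnote to Table 3.3 with two parts. First, row 1 (reduce by one dose level) governs whenever an ANC below 500 lasts more than 7 days, with or without fever or infection. Second, where any other rows or clauses overlap, the dose reduction applies, and the rule on two consecutive missed Day 8 doses is kept for every ANC below 1000. The clinical team should confirm the wording.

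Limiting rows 4 to 6 to ANC 500 to 999 would be a poorer repair, because it would drop the missed-Day-8 reduction for counts below 500.

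The cost is one footnote through a protocol amendment, with no added visits or tests. The downside is that a few more participants may have a mandatory, irreversible one-level reduction. The current version ends further long-term follow-up, and the documents do not say whether anyone is still on eribulin. If nobody is, the change matters only where this table is reused.

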5.2 Pre-Treatment Criteria

5.2.1 Cycle 1, Day 1

Criteria to treat on Cycle 1 Day 1 (Patient does not need to re-meet full eligibility criteria):

- Absolute neutrophil count $>1500/\text{mcL}$
- Platelets $>100,000/\text{mcL}$
- ALT and AST $<2.5 \times \text{ULN}$ in a participant with no documented liver metastases; ALT and AST $<5.0 \times \text{ULN}$ in a participant with documented liver metastases
- Total bilirubin $<1.5 \times \text{ULN}$ ($2.0 \times \text{ULN}$ in a participant with well documented Gilbert's syndrome)

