5.2.2 Cycle 1, Day 8 and Day 8 of subsequent cycles

Criteria to treat on Cycle 1 Day 8 and Day 8 of subsequent cycles:

- Absolute neutrophil count $>1000/\text{mcL}$
- Platelets $>100,000/\text{mcL}$
- ALT and AST $<2.5 \times \text{ULN}$ in a participant with no documented liver metastases; ALT and AST $<5.0 \times \text{ULN}$ in a participant with documented liver metastases
- Total bilirubin $<1.5 \times \text{ULN}$ ($2.0 \times \text{ULN}$ in a participant with well documented Gilbert's syndrome)

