5.2.3 Day 1 of subsequent cycles

Criteria to treat on Day 1 of subsequent cycles:

- Absolute neutrophil count $>1000/\text{mcL}$
- Platelets $>100,000/\text{mcL}$
- ALT and AST $<2.5 \times \text{ULN}$ in a participant with no documented liver metastases; ALT and AST $<5.0 \times \text{ULN}$ in a participant with documented liver metastases
- Total bilirubin $<1.5 \times \text{ULN}$ ($2.0 \times \text{ULN}$ in a participant with well documented Gilbert's syndrome)

Any non-hematologic toxicities must return to baseline or to $< \text{Grade } 2$ beginning with Day 1 of each cycle.

If dose is held or missed on Day 1 of a cycle, that cycle will not be considered to start until the day the dose is actually administered to the patient (ie, D1-D8-rest, X-D1-D8-rest, etc.)

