≤ Grade 1	No dose modification
Grade 2	Hold eribulin until recovery to grade < 2.
Grade 3	Hold eribulin until recovery to grade < 2 then reduce by 1 dose level.
Grade 4	Hold eribulin until recovery to grade < 2 then reduce by 1 dose level.

Table 3.5 Eribulin Anemia Dose Modification

Anemia	Management/Next Dose for Eribulin
≤ Grade 1	No dose modification
Grade 2	No dose modification
Grade 3	No dose modification
Grade 4	Hold eribulin until recovery to grade < 2 then reduce by 1 dose level. PRBC transfusions are permitted to treat anemia on protocol.

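### Sections 5.2.2/5.2.3 and Tables 3.3/3.4 set different blood-count levels for restarting eribulin after a hold, in opposite directions for neutrophils and platelets, and do not say whether both must be met

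*Combined protocol and SAP*

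**What the plan says.** Section 5.2 gives count criteria for treating. Cycle 1 Day 1 (5.2.1) needs an ANC above 1500/mcL. Section 5.2.2, headed "Criteria to treat on Cycle 1 Day 8 and Day 8 of subsequent cycles", and Section 5.2.3, headed "Criteria to treat on Day 1 of subsequent cycles", both need an ANC above 1000/mcL and platelets above 100,000/mcL. Section 5.2.3 adds a grade-based recovery rule, but only for other toxicities: "Any non-hematologic toxicities must return to baseline" or to below Grade 2.

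Section 6.1 gives the hold rules for eribulin, in grades:
- **Table 3.3 (neutropenia).** The triggers are ANC below 500, ANC below 1000 with fever or infection, and ANC below 1000 without either. Every row carries the instruction "Hold eribulin until recovery to grade < 2". The rows differ in what follows: same dose, reduced dose, growth factor support. The uncomplicated row reads "First occurrence: Hold eribulin until recovery to grade < 2 then resume at the same dose".
- **Table 3.4 (thrombocytopenia).** Grade 1 or lower needs no dose modification. Grades 2, 3 and 4 are held until recovery below grade 2, with a dose reduction after Grades 3 and 4.

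Section 6 and the notes to Table 2 say that grades follow CTCAE version 5.0. The cut-offs are not printed. The same notes say that a Day 8 dose for which the criteria are not met is skipped and not made up.

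**The concern.** Both sets of rules decide whether a given eribulin dose is given. One set is written as counts and the other as grades, and they do not appear to meet at the same point. If so, a participant coming off a hold can satisfy one section and fail the other on the same day.

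What is at stake is dosing and safety handling in participants recovering from neutropenia or thrombocytopenia. The same count could lead one investigator to treat and another to wait or skip, and either could be charged with a deviation under the section not followed. The choice can carry forward: a skipped Day 8 dose is not made up, and under Table 3.3 two consecutive Day 8 doses missed for uncomplicated neutropenia lead to a dose reduction, which Section 6.1 does not allow to be reversed.

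**Working it through.** The plan states no figure on this point, so there is nothing to reproduce. The check compares the two rules over a range of counts.

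**Inputs from the documents**
- Sections 5.2.2 and 5.2.3: treat if ANC > 1000 and platelets > 100,000.
- Tables 3.3 and 3.4: a hold ends at grade < 2, that is, at a count at or above the lower limit (floor) of grade 1.

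**Assumption.** The floors of grade 1 are ANC 1500/mcL and platelets 75,000/mcL. They belong to the scale the protocol names but are not printed in it, so they are varied below.

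**Step 1: neutrophils, in a participant who has met a Table 3.3 trigger**

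| ANC on a later dosing day | Sections 5.2.2/5.2.3 | Table 3.3 |
|---|---|---|
| 1000 or less | not permitted | held |
| above 1000 and below 1500 | permitted | still held |
| 1500 or more | permitted | hold ended |

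The middle row is the mismatch, 1500 − 1000 = 500/mcL wide. Example: a participant held for an ANC below 1000 returns on the next Day 1 at 1200. Section 5.2.3 is met and Table 3.3 is not.

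**Step 2: platelets, in a participant who has met a Table 3.4 hold**

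| Platelets on a later dosing day | Sections 5.2.2/5.2.3 | Table 3.4 |
|---|---|---|
| below 75,000 | not permitted | held |
| 75,000 to 100,000 | not permitted | hold ended |
| above 100,000 | permitted | hold ended |

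This band is 100,000 − 75,000 = 25,000/mcL wide. Table 3.3 is the stricter rule for neutrophils and Section 5.2 is the stricter rule for platelets, so neither section is consistently the more cautious.

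**Step 3: dependence on the assumed floors**

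| Assumed ANC floor of grade 1 | Mismatch band |
|---|---|
| 1000 | none, apart from the value 1000 itself |
| 1250 | above 1000, below 1250 |
| 1500 | above 1000, below 1500 |
| 1750 | above 1000, below 1750 |
| 2000 | above 1000, below 2000 |

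| Assumed platelet floor of grade 1 | Mismatch band |
|---|---|
| 50,000 | 50,000 to 100,000 |
| 75,000 | 75,000 to 100,000 |
| 90,000 | 90,000 to 100,000 |
| 100,000 | none, apart from the value 100,000 itself |
| 125,000 | reversed: above 100,000, below 125,000 |

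The rules coincide only if the grade 1 floors are exactly 1000 and 100,000. Other floors change the width of the band, or its direction for platelets, but do not remove it.

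**Step 4: who is outside the neutrophil mismatch**
- A participant whose ANC falls to 1200 without having gone below 1000 meets no row of Table 3.3 and is handled by Section 5.2 alone.
- Cycle 1 Day 1 has its own criterion (ANC > 1500) and no earlier eribulin toxicity on study to recover from.

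**Step 5: does any sentence reconcile the two?** Section 5.2.3 confines its grade-based rule to non-hematologic toxicity, so within Section 5.2 the numeric cut-offs alone apply to counts. Section 5.1 refers dose modifications to Section 6, and Section 6.1 says eribulin toxicities should be managed by Tables 3.1 to 3.5. No sentence says that both conditions must be met, or which gives way.

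**The case against.** The strongest reply is that these are two stacked rules and not two competing ones. Section 5.2 is a routine gate for everyone. Tables 3.3 and 3.4 apply only after a toxicity has occurred, and Sections 5.1, 6 and 6.1 all direct toxicity management to the tables. On that reading, meeting Section 5.2.3 does not cancel a hold already in force. Section 6.1 also presupposes separate Day 8 criteria when it says what to do if they are not met. For platelets, the absence of a dose modification at Grade 1 may mean only that the dose level is unchanged. A participant at 80,000 on Day 8 would then skip the dose without a reduction, and both sections would be obeyed. Section 6.1 leaves room for clinical judgement as well.

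Much of this stands. The cumulative reading is workable and may be what was meant. It also limits the point: a reader might infer that any participant with an ANC of 1200 is treated under one section and held under the other, and that is not so without an earlier Table 3.3 trigger. The Grade 1 row of Table 3.4 is not a clear instruction to treat, so the platelet point rests on the rows for Grades 2 to 4, which do set a hold-release level.

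The reply does not close the gap. The cumulative rule has to be supplied by the reader. The cross-references point to Section 6 for toxicity, yet for platelets it is Section 5.2 that would have to prevail. Clinical judgement does not tell a site which of two written criteria it will be held to.

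**Conclusion.** This is an internal inconsistency between sections, not a design choice. The text alone shows that Section 5.2 uses counts and Tables 3.3 and 3.4 use grades, with no stated link. The size of the gap rests on the assumed CTCAE v5.0 floors: for neutrophils, above 1000 and below 1500/mcL during recovery from a Table 3.3 trigger; for platelets, 75,000 to 100,000/mcL, in the opposite direction. The consequence is inconsistent dosing and safety handling of recovering participants.

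Two stronger conclusions might be drawn, and the documents support neither.
- **That the number affected can be estimated.** A reader might apply the 30.8% rate of Grade 3 or 4 neutropenia in Section 2.6 to the 57 planned participants. That figure is a rate over the whole of treatment in a breast cancer trial. The documents give no distribution of counts on dosing days after a hold, and Table 3.3 calls for growth factor support that would shift those counts.
- **That the regimen or the week-12 endpoint is left undefined.** Section 5.1 keeps restaging on schedule when treatment is delayed, Section 13.9.2 makes the efficacy analyses intent-to-treat, and Section 13.9.1 counts toxicity in anyone treated, regardless of dose or duration. The rule of at least 9 of 19 is unaffected. Some variation in delivered eribulin is already built into the dose-modification rules.

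**What to change.** Reconcile Sections 5.2.2 and 5.2.3 with Tables 3.3 and 3.4. Express the level for treating and the level for ending a hold in the same units; counts per mcL would remove the dependence on cut-offs that are not printed. Then state either that both conditions must be met or which section governs after a hold, with a cross-reference in each place. In Table 3.4, say whether the Grade 1 entry concerns the dose level only. The clinical team must choose the values; this review takes no view on them.

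The cost is a wording amendment. It needs no additional participants, data or analysis.
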